5.6.1. Extent of Exposure

Because of the different route and frequency of treatment administration across the 4 agents (for JNJ-3989 one subcutaneous injection every 4 weeks (Q4W), for JNJ-6379 once daily tablets (QD), for NA once daily tablet (QD), and for PegIFN- α 2a one subcutaneous injection weekly (QW)) the total duration of exposure (weeks) will be calculated for each agent as follows:

- JNJ-3989: $[\text{Min} ((\text{Date of last JNJ-3989 injection in the given phase} + 27 \text{ days}), \text{Date of trial disposition, cut-off date}) - \text{Date of first JNJ-3989 injection in the given phase} + 1] / 7$
- NA: $[\text{Min} (\text{Date of the last NA administration in the given phase, Date of discontinuation from NA, Date of trial disposition, Date of clinical cut-off}) - \text{Date of first NA administration date in the given phase} + 1] / 7$
- PegIFN- α 2a: $[\text{Min} (\text{Date of the last PegIFN-}\alpha\text{2a injection} + 6 \text{ days, Date of discontinuation from PegIFN-}\alpha\text{2a, Date of trial disposition, cut-off date}) - \text{Date of first PegIFN-}\alpha\text{2a injection} + 1] / 7$

The total duration of exposure (weeks) to JNJ-6379 will be calculated for participants who received JNJ-6379 as follows:

- JNJ-6379: $[\text{Min} (\text{Date of the last JNJ-6379 administration in the given phase, Date of treatment disposition for JNJ-6379, Date of trial disposition, Date of clinical cut-off}) - \text{Date of first JNJ-6379 administration in the given phase} + 1] / 7$

Cutoff dates will be defined to match the prespecified timepoints for DRC periodical data reviews, interim analyses and the primary analysis, respectively (see Section 5.8).

Descriptive statistics for duration of each study treatment within a study intervention (N, mean, SD, median, and range (minimum, maximum)) during the 24 weeks of treatment (treatment period 1 and 2) will be summarized. The duration of treatment with NA will be summarized also for the FU phase. Those participants who stopped NA treatment at or before Week 24 and never restarted NA treatment thereafter will be counted as having zero weeks of NA exposure during the FU phase.

The number and percentage of participants who skipped any dose of JNJ-3989 or JNJ-6379 or NA or PegIFN- α 2a will be summarized separately for each study intervention. Additionally, the number and percentage of participants who missed 2 or more JNJ-3989 injections, or who missed more than 5 JNJ-6379 doses within a four-week period, or who missed more than 5 doses of NA within a four-week period or who missed 2 or more PegIFN- α 2a injections will be presented.

Study intervention compliance will be summarized descriptively. See [Appendix 7](#) for further details.

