 - qq. *Visits at follow-up Week 16, 20, 28, 32, 40, and 44 are optional for participants who continue NA treatment and for participants who have restarted NA treatment during the follow-up period, provided that their HBV DNA and ALT values are stable.*
 - rr. Liver function tests only.
 - ss. Urine pregnancy tests will be provided to the participants for at home use as necessary to ensure urine pregnancy tests are performed at least every 4 weeks. Participants will report the results to the study site personnel at the next visit, and these will be added to the source documents. If positive, the participant should contact the site immediately.
 - tt. No JNJ-3989/PegIFN- α 2a will be administered or dispensed during follow-up. Administration/Dispensation of NA is only applicable for participants who could not stop NA treatment, or for those who met the NA re-treatment criteria. In between study visits, participants will take NA at home and they will bring their NA treatment with them to each study visit.
 - uu. If the NA treatment completion criteria are met at Week 24, treatment with NA will be stopped at FU Week 2.
 - vv. Available historical data on HBeAg status before start of NA treatment will be collected in the CRF.
 - ww. A urinalysis and urine chemistry sample will be taken at FU Week 2. In case of abnormalities, the tests should be repeated at the following visits.
 - xx. Includes close monitoring for neuropsychiatric adverse events during the PegIFN- α 2a treatment period. Participants who develop a neuropsychiatric adverse event during PegIFN- α 2a treatment, will be monitored closely until the neuropsychiatric adverse event resolves, with frequent (at least weekly) follow-up phone calls.
 - yy. NA treatment should be re-started in accordance with the NA re-treatment criteria (see Section 6.7.1, NA Re-treatment Criteria and Monitoring After Stopping of NA and Section 10.12 Appendix 12, for guidance after stopping NA treatment).
 - zz. Participants enrolled before Protocol Amendment 3 was in effect, may have received JNJ-6379 as part of their study intervention.

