- Any investigational agent, investigational vaccine, invasive investigational medical device, or investigational biological product (other than the study intervention taken in the context of this study).
Note: Approved COVID-19 vaccines or COVID-19 vaccines with conditional marketing authorization, emergency use authorization or special approval for emergency are allowed.

Disallowed from 6 months prior to baseline until end of follow-up:

- Any systemically (eg, intravenously, intramuscularly, orally, subcutaneously) administered medication that directly or indirectly interferes with immune responses (eg, cyclosporine, interleukins, systemic corticosteroids exceeding 5 mg of prednisolone equivalent/day).

Disallowed from screening until end of follow-up:

- Any anti-HBV drug (including vaccines) other than the study intervention taken in the context of this study.
Note: NA standard of care treatment is allowed between screening and baseline.
- Biotin (>1 mg daily dose), either taken alone or as part of a multivitamin formulation.
Note: The use of other vitamins is allowed.
- Topical steroids (>7 days) under occlusive dressing.

Note: The list of disallowed concomitant medication is not exhaustive; for products falling in one of the categories and not mentioned by name, the sponsor should be contacted to determine whether the product can be allowed.

The prescribing information for ETV, tenofovir disoproxil, TAF, and PegIFN- α 2a should be consulted for any additional prohibited medication. In case of flu-like symptoms after administration of PegIFN- α 2a, paracetamol up to a maximum of 2 g per 24 hours and a maximum of 6 g per week is allowed.

Medications requiring subcutaneous injection (other than JNJ-3989 and PegIFN- α 2a; eg, insulin) should be administered away from the JNJ-3989 and PegIFN- α 2a injection sites.

6.6. Study Intervention Completion at Week 24

With the implementation of Protocol Amendment 3, all participants had to stop JNJ-6379 treatment immediately.

Participants will stop treatment with JNJ-3989 and PegIFN- α 2a at Week 24 (EOSI). If all of the following NA treatment completion criteria are met at Week 24, treatment with NA will also be stopped at the next scheduled visit (ie, FU Week 2):

- The participant has ALT $<3x$ ULN, AND
- The participant has HBV DNA $<LLOQ$, AND
- The participant is HBeAg-negative, AND
- The participant has HBsAg <10 IU/mL.

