6.7. Dose Modification

Dose modifications of JNJ-3989 and NA (increase or decrease of dose level) are not allowed during the study.

For PegIFN- α 2a, dose adjustment guidelines are applicable for participants who develop laboratory abnormalities during PegIFN- α 2a treatment, as recommended in the locally approved prescribing information for PegIFN- α 2a and upon investigator's assessment.

In exceptional circumstances (ie, laboratory abnormalities during PegIFN- α 2a treatment) the use of a local laboratory may be considered in parallel to the central laboratory testing, at the study investigator's discretion, to obtain rapid results to ensure patient safety. If applicable, a copy of the local laboratory report should be reviewed by the investigator and filed with the source documents, along with reference ranges.

For participants who prematurely discontinue PegIFN- α 2a, treatment with PegIFN- α 2a may be restarted according to the recommendations from the locally approved prescribing information for PegIFN- α 2a.

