6.7.1. NA Re-treatment Criteria and Monitoring After Stopping of NA

Participants who meet the protocol-defined NA treatment completion criteria outlined in Section 6.6, Study Intervention Completion at Week 24, will be monitored closely during the FU Period.

After stopping NA treatment, participants should be monitored as follows:

- Regular monitoring visits will be every 4 weeks during the follow-up phase in accordance with the [Schedule of Activities](#).
- A post-treatment HBV DNA value of >20,000 IU/mL should trigger re-testing of ALT/AST, HBV DNA, and total and direct bilirubin within a maximum of 7 days from receipt of the data and further repeats as necessary (ie, weekly until HBV DNA returns to <20,000 IU/mL).
- A post-treatment HBV DNA value of >2,000 IU/mL (but <20,000 IU/mL) should trigger a re-test within 14 days from receipt of the data and further repeats as necessary (ie, every other week until HBV DNA returns to <2,000 IU/mL).
- A post-treatment ALT value of >5x ULN should trigger re-testing of ALT, AST, ALP, total and direct bilirubin, INR, albumin, and HBV DNA on a weekly basis until ALT and AST levels have returned to <5x ULN.

After stopping NA treatment, participants should re-start NA treatment:

- Immediately with signs of decreasing liver function based on laboratory findings (eg, INR, direct bilirubin) or clinical assessment (eg, ascites, hepatic encephalopathy).
- Immediately with an HBV DNA value of >100,000 IU/mL (irrespective of confirmation and/or ALT increase).
- With confirmed post-treatment HBeAg seroreversion (HBeAg positive after it was negative at NA completion).
- With confirmed* post-treatment increases in HBV DNA >2,000 IU/mL and ALT >5x ULN.

- With confirmed* post-treatment increases in HBV DNA >20,000 IU/mL.

* *At least 4 weeks apart – frequency of visits as described above*

Note: Additional re-testing and/or earlier restarting of NA treatment is at the investigator's discretion, even if the above cut-offs are not yet met.

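### SAP 5.6.1 computes follow-up NA exposure as one span, so it is wrong for participants who stop NA at FU Week 2 and are re-treated later in follow-up

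*SAP*

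**What the plan says.** **Formula.** SAP 5.6.1 ends NA exposure at the minimum of "Date of the last NA administration in the given phase, Date of discontinuation from NA, Date of trial disposition, Date of clinical cut-off". It subtracts the "Date of first NA administration date in the given phase", adds 1 and divides by 7. There is no term for an off-drug gap and no sum over episodes. The SAP does not say which stop the discontinuation date means when there is more than one.

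**Use in follow-up.** The same section states: "The duration of treatment with NA will be summarized also for the FU phase".

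**Only special rule.** "Those participants who stopped NA treatment at or before Week 24 and never restarted NA treatment thereafter will be counted as having zero weeks" of follow-up NA exposure. Nothing is said about participants who restart.

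**When NA stops.** Protocol 1.3 (Schedule of Activities footnote): "If the NA treatment completion criteria are met at Week 24, treatment with NA will be stopped at FU Week 2". Protocol 6.6 says the same.

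**Restart.** Protocol 6.7.1 introduces its triggers with "After stopping NA treatment, participants should re-start NA treatment". Some triggers act immediately; others need confirmation at least 4 weeks apart.

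**Phase boundary.** In SAP Table 3, follow-up begins the day after the end of the treatment periods. That end is set by study-agent intake or discontinuation and the Week 24 visit. SAP 5.1 leaves NA out of the study agents, so NA taken after Week 24 does not extend the treatment phase.

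**The concern.** A participant who meets the completion criteria takes NA for about the first two weeks of follow-up, has an NA-free interval, and may then restart. Both NA episodes lie in one analysis phase, and the first NA date in that phase is about FU Day 1. The formula can be read in two ways:

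- **Reading A:** the discontinuation date is absent or is the final stop. The span then runs from first to last dose, and the NA-free interval counts as exposure.
- **Reading B:** the discontinuation date is the FU Week 2 stop. The minimum then cuts exposure there, and all re-treatment time is lost.

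Under A, a re-treated participant is reported like someone who never stopped NA. Under B, the same participant is reported like someone who was never re-treated. At stake is whether the follow-up NA exposure table describes the re-treated participants correctly, and whether two programmers working from the same text would produce the same table.

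**Working it through.** The documents state no exposure figure to reproduce, so the check applies the SAP formula to the target days in SAP Table 4.

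**Inputs**
- First NA date in follow-up: FU Day 1 (NA continues daily after Week 24).
- NA stop: FU Week 2, target FU Day 15.
- Restart: FU Day R.
- Last NA date: FU Week 48, target FU Day 337 (assumes re-treatment continues to the end of follow-up).

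**Formulas, in weeks**
- True exposure, two episodes: [(15 − 1 + 1) + (337 − R + 1)]/7 = (353 − R)/7.
- Reading A: (337 − 1 + 1)/7 = 48.1, whatever R is.
- Reading B: (15 − 1 + 1)/7 = 2.1, whatever R is.
- Error under A: (R − 16)/7 over. Error under B: (338 − R)/7 under.

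**Results** (differences taken before rounding)

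| Restart | FU Day R | True | A gives | A over by | B gives | B under by |
|---|---|---|---|---|---|---|
| FU Week 4 | 29 | 46.3 | 48.1 | 1.9 | 2.1 | 44.1 |
| FU Week 8 | 57 | 42.3 | 48.1 | 5.9 | 2.1 | 40.1 |
| FU Week 12 | 85 | 38.3 | 48.1 | 9.9 | 2.1 | 36.1 |
| FU Week 24 | 169 | 26.3 | 48.1 | 21.9 | 2.1 | 24.1 |
| FU Week 36 | 253 | 14.3 | 48.1 | 33.9 | 2.1 | 12.1 |
| FU Week 44 | 309 | 6.3 | 48.1 | 41.9 | 2.1 | 4.1 |

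The two readings differ by (337 − 15)/7 = 46.0 weeks for the same person.

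**Sensitivity to the visit window.** With restart on Day 169 and the stop moved by the 4-day window to Day 11 or Day 19, true exposure is 25.7 or 26.9 weeks. The error under A is then 22.4 or 21.3 weeks, and under B it stays at 24.1.

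**Size in months** (1 month = 30.4375 days). Under A the error reaches one month only for a restart on FU Day 47 or later. Under B it reaches one month only for a restart on FU Day 307 or earlier.

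**NA stopped before follow-up and restarted within it.** Protocol 6.6 makes this possible after early discontinuation. With restart on Day 169, the truth is (337 − 169 + 1)/7 = 24.1 weeks, and A gives exactly that. B, with the stop on the day before FU Day 1, gives (0 − 169 + 1)/7 = −24.0 weeks, an impossible value.

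**The zero-week rule.** It covers participants who stopped at or before Week 24. Completers stop at FU Week 2, which is Week 26 in SAP Table 4. A completer who never restarts therefore has 15/7 = 2.1 weeks by formula and is not literally covered by the rule.

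**The case against.** The strongest reply is that little depends on this number. A reader might infer that the error distorts the comparison of treatment-free with NA-covered follow-up, and so the flare, re-treatment and functional cure results. The documents do not support that. SAP 5.1.11 ends the off-treatment period when NA re-treatment starts. SAP 5.4.1.1.2 identifies restarts from the NA study-drug administration CRF page. Off-treatment seroclearance, functional cure and partial cure (5.4.1.1.4, 5.4.1.1.5, 5.4.1.1.14) are conditioned directly on no restart or re-treatment. Virologic flares can end at NA restart (5.4.1.1.16), and analyses in 5.4.1.3 censor at NA re-treatment. None uses the 5.6.1 duration. This part of the reply stands.

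A reader might also infer that every re-treated participant is wrong by months. That fails too. A restart at FU Week 4 is over by 1.9 weeks under A, a restart at FU Week 44 is under by 4.1 weeks under B, and NA stopped before follow-up is counted exactly under A. Only one reading would be programmed.

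A third inference is that PegIFN-α2a interruptions go unreported. Protocol 6.7 does allow a restart, since PegIFN-α2a "may be restarted according to the recommendations from the locally approved prescribing information", and the PegIFN duration formula is also a single span. But SAP 5.6.1 reports skipped doses and participants who missed 2 or more injections, and the Appendix 7 compliance ratio (injections received out of 12) falls with each missed injection. Interruptions are therefore visible.

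What the reply does not remove is the formula itself. For a completer who stops at FU Week 2 and restarts later, neither reading returns the time on NA. No other SAP summary supplies it: Appendix 7 compliance excludes NA, and the re-treatment tables count participants, not weeks.

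**Conclusion.** The point holds in a limited form. As written, SAP 5.6.1 gives a wrong follow-up NA exposure for participants who meet the completion criteria, stop at FU Week 2 and are re-treated later in follow-up. For a restart at FU Week 24 the error is about five months in either direction. The zero-week rule does not match the protocol's stop date, so completers who never restart are not clearly handled either.

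The consequence is confined to one descriptive safety summary. The primary endpoint, the efficacy, flare and re-treatment endpoints, and NA exposure in Treatment Periods 1 and 2 are untouched. The documents do not say how many participants would stop NA or be re-treated; it is some subset of approximately 50.

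The figures assume target visit days, daily NA intake within each episode, and re-treatment continued to FU Day 337.

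**What to change.** In SAP 5.6.1:

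1. Define follow-up NA exposure as the sum, over NA episodes in the phase, of (episode end − episode start + 1)/7, taken from the NA study-drug administration CRF page that SAP 5.4.1.1.2 already uses to identify restarts.
2. Date NA discontinuation per episode.
3. Reword the zero-week rule to match the FU Week 2 stop, stating whether a completer who never restarts is reported with the roughly two weeks actually taken or with zero.

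Optional minor additions: exclude documented off-drug gaps from PegIFN-α2a duration in 5.6.1, and in Appendix 7 limit PegIFN-α2a compliance to participants who started it, as is already done for JNJ-6379.

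The cost is SAP wording and minor programming, with no new data collection. Reported exposure may be lower than under a first-to-last-dose calculation.

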5.6.2. Adverse Events

The verbatim terms used in the CRF by investigators to identify adverse events will be coded using the Medical Dictionary for Regulatory Activities (MedDRA version 21.1 or higher). Any AE occurring at or after the initial administration of study intervention is considered to be treatment emergent. If the event occurs on the day of the initial administration of study intervention, and

either event time or time of administration are missing, then the event will be assumed to be treatment emergent. If the event date is recorded as partial or completely missing, then the event will be considered to be treatment emergent unless it is known to be prior to the first administration of study intervention based on partial onset date or resolution date. All reported treatment-emergent adverse events will be included in the analysis. For each adverse event, the number and percentage of participants who experience at least 1 occurrence of the given event will be summarized.

Summary tables and listings will be provided for treatment-emergent adverse events:

- AEs
- Serious AEs (SAEs)
- AEs leading to discontinuation of any study agent within a study intervention including NA
- AEs by relationship to each study agent within a study intervention including NA

In addition to the summary tables, listings will be provided for participants who experienced any:

- SAEs
- AEs leading to discontinuation of each study agent within a study intervention including NA

For participants reporting rash, a listing with specific grade will be provided.

Incidence of treatment-emergent adverse events of special interest will be summarized by analysis phase and overall.

The adverse events of special interest include:

- ALT/AST elevations
- Injection Site Reactions Related to JNJ-3989
- Renal Complications
- Cholesterol increase
- Hematologic abnormalities (platelet count, hemoglobin, reticulocytes, neutrophil count)

The list of all preferred terms belonging to ALT/AST elevation, renal complication, cholesterol increase, and hematologic abnormalities is provided in [Appendix 8](#). Injection site reactions will be identified using the eCRF Injection Site Reaction form.

A listing of participants who died will be provided.

5.6.3. Additional Safety Assessments

5.6.3.1. Clinical Laboratory Tests

Laboratory data will be summarized by category of laboratory test. The different categories and laboratory tests used in the analysis are listed in [Table 7](#).

Table 7: Laboratory Parameters

Laboratory Assessments	Parameters	
Hematology	Platelet count Red blood cell count Hemoglobin Hematocrit	RBC Indices: MCV MCH % Reticulocytes White Blood Cell (WBC) count with Differential: Neutrophils Lymphocytes Monocytes Eosinophils Basophils

Note: A WBC evaluation may include any abnormal cells, which will then be reported by the laboratory. An RBC evaluation may include abnormalities in the RBC count, RBC parameters, or RBC morphology, which will then be reported by the laboratory. In addition, any other abnormal cells in a blood smear will also be reported.
		
Hematology Coagulation	Activated partial thromboplastin time Prothrombin Intl. normalized ratio Prothrombin time	
Clinical Chemistry	Sodium Potassium Chloride Bicarbonate Blood urea nitrogen (BUN) Creatinine Glucose Aspartate aminotransferase (AST) Alanine aminotransferase (ALT) Gamma-glutamyltransferase (GGT) α_1 -acid glycoprotein Calculated creatinine clearance (by CKD-EPI formula) (i.e. eGFR calculation based on Creatinine) Fibrinogen (on blood) Cystatin C eGFR calculation based on Cystatin C	Total, direct, indirect bilirubin Alkaline phosphatase Creatine phosphokinase (CPK) Lactic acid dehydrogenase (LDH) Uric acid Calcium Phosphate Albumin Total protein Total cholesterol High-density lipoprotein cholesterol Low-density lipoprotein cholesterol Triglycerides Magnesium Lipase Amylase (reflex testing of pancreatic amylase should be done in case of amylase or lipase increase from screening onwards)
Routine Urinalysis	Dipstick Specific gravity pH Glucose Protein Blood Ketones Bilirubin Urobilinogen Nitrite Leukocyte esterase	Sediment (if dipstick result is abnormal) Red blood cells White blood cells Epithelial cells Crystals Casts Bacteria

In case of a positive dipstick result, a urine sample will be set aside for additional examination of the positive parameter (eg, quantification as applicable).
		
Urine Chemistry (quantitative measurement)	Creatinine Sodium Phosphate	Glucose Protein Albumin

Table 7: Laboratory Parameters

Laboratory Assessments	Parameters
Renal Biomarkers	Retinol binding protein Beta-2-microglobulin Note: Other biomarkers might be measured.
Thyroid Function Tests	Thyroid Stimulating Hormone (TSH) Thyroxine (T4)

Clinical laboratory tests will be summarized using safety analysis set for chemistry, hematology, urinalysis and renal biomarkers panels.

Descriptive statistics (n, mean, SD, minimum, median, and maximum) will be calculated for each laboratory parameter for observed values and changes from baseline at each scheduled time point by analysis phase.

Shift tables will be provided summarizing the shift in laboratory values from baseline over time with respect to abnormality criteria (low, normal, high) for each laboratory parameter by analysis phase.

Descriptive statistics and graphical displays will be presented for all chemistry, hematology, and urinalysis laboratory tests at scheduled time points.

Change from baseline over time will be summarized for chemistry, hematology, urinalysis tests, and renal biomarkers.

Abnormality criteria (based on the criteria specified in the DAIDS Toxicity Grading Scale (see Clinical Protocol Appendix 9, DAIDS Table) will be applied to baseline and postbaseline values or in accordance with the normal ranges of the clinical laboratory if no gradings are available.

Postbaseline abnormalities will be compared with their corresponding baseline result:

- For toxicity grades, treatment emergent will be concluded if the postbaseline grade is worse than the baseline grade.
- For abnormalities based on normal range and/or criteria: If the postbaseline value is above the upper limit and the baseline value is below the upper limit (eg, Normal or Low), then the postbaseline abnormality will be considered TE. The same applies to the postbaseline value being below the lower limit with the baseline value being above the lower limit (eg, Normal or High).
- If the baseline value is missing, a postbaseline abnormality will always be considered as TE.

For each lab parameter, a worst-case analysis will be performed by using the worst abnormality and/or worst toxicity grade lab value and time point per participant. The worst toxicity case is the value associated to the highest toxicity grade and is derived per parameter and toxicity direction (hypo / hyper). Worst-case will be derived within each analysis phase, including unscheduled assessments. For abnormalities, in case the same participant has both abnormalities (low and high)

for the same lab test within the same phase, the participant will be counted in the analysis for both toxicity directions (abnormally high and low).

Imputation rules:

In case continuous laboratory results are not numerically expressed, but as a character (e.g. 'less than 2', '>25'), these results will be numerically imputed as follows:

- If the analysis result contains '<' then the result will be multiplied by 0.999 (e.g. <6.1 becomes 6.0939).
- If analysis result contains '>' then the result will be multiplied by 1.001 (e.g. >6.1 becomes 6.1061).
- If analysis result contains '≤' or '≥' then only the numeric portion of the result will be used.

This also applies to normal limits expressed as such.

Shift tables will be provided summarizing the shift in laboratory values from baseline over time with respect to abnormality criteria (low, normal, high) for each laboratory parameter by analysis phase.

The cross-tabulations of the worst toxicity grades over time versus baseline grade and the worst abnormalities versus baseline grade per parameter and per analysis phase will be presented also including the number of participants per worst grade and the number of participants per abnormality.

A tabulation of percentage and number of the participants who have treatment-emergent worst toxicity grades and treatment-emergent worst abnormalities per parameter and analysis phase will be included. The incidence table of worst toxicity grade abnormality in laboratory parameters will be also presented stratified by the subgroups of interest identified in Section 5.7.5.2.

Plots of mean (+/- SE) values and changes from baseline over time for selected laboratory parameters will be presented. Spaghetti-plots for selected laboratory parameters will be presented over time (with Week shown on x-axis).

A listing including all parameters with at least one treatment-emergent toxicity or abnormality per participant (exclusion of urinalysis) will be generated.

